9.1 Discontinuation of Study Intervention

Participants may voluntarily discontinue receiving MTMs and/or remotely delivered nutritional counseling for any reason at any time. However, a member of the KPNC DOR research team will contact the participant before discontinuation to evaluate any issues related to the study meals or enhanced nutritional counseling and answer any questions before confirming their decision to discontinue study intervention.

9.2 Withdrawal from the Study

Participants may voluntarily withdraw consent to participate in the study for any reason at any point in time.

However, withdrawal of consent occurs only when all of the following criteria are met:

- The participant states they do not want to participate in the study any further
- The participant states they do not want any further follow-up visits (i.e., telephone encounters) or assessments
- The participant states they do not want any further study-related contacts

At the time a participant formally withdraws consent for study participation, a member of the KPNC DOR research staff will document the participant's decision and primary reason for study withdrawal in the Appian-based study online tracking system. If relevant, the study intervention will be discontinued and no further assessments conducted. Further attempts to contact the participant are not allowed.

9.3 Loss to Follow-up

For participant's whose status is unclear because they fail to complete study contacts without stating an intention to withdraw, the KPNC DOR research team will show due diligence by attempting to contact the participant, the participant's family and/or listed secondary contact(s), or KPNC primary treating physician. The KPNC DOR research team will also continue to monitor the participant's KPNC EHR data as agreed in the informed consent and will also document in the Appian-based study online tracking system all of the steps taken to contact the participant (i.e. dates of telephone calls, etc.). A participant should not be formally considered lost to follow-up until his/her scheduled end of study visit would have occurred. Outcome data for endpoint ascertainment should be available for all participants with active KPNC membership status.

9.4 Early Termination of the Study

The study may be terminated at the sole discretion of the Sponsor (i.e., KPNC DOR) for any reason, including medical or ethical reasons affecting the continued performance of the study, or the inability to effectively recruit participants. If this occurs, the Sponsor will notify the KPNC IRB, co-investigators, and any regulatory authorities, as appropriate.

9.5 Study End

End of Study will occur when the last participant discharged has 90-day clinical outcomes extracted, has withdrawn consent, or has died, whichever comes first.

10 Study Assessments and Procedures

10.1 Baseline Assessments and Follow-up

Patient demographic characteristics and baseline information on clinical characteristics will be automatically abstracted from the KPNC EHR by the study analyst after obtaining IRB approval but before pre-randomization. These data will include, but not be limited to, date of birth, sex, race/ethnicity, and relevant past medical history.

The study will be conducted between April 27, 2020 and September 29, 2021. End of Study will occur when the last enrolled participant discharged home has completed 90-day follow-up for clinical outcomes, has withdrawn consent, or has died, whichever comes first.

PROJECT YEAR	2020	2021	
Obtain IRB approvals			
Finalize protocol			
Identify and enroll participants			
Follow-up			
Data analyses			
Submit primary manuscript			
Project close-out			

Note: Each box represents a time interval of 6 months.

10.2 Primary Outcome

The primary outcome will be readmissions for any cause within 90 days after discharge from the index hospitalization. A readmission is defined as a non-elective hospitalization lasting >23 hours. All readmissions will be assessed passively using the KPNC EHR which comprehensively captures network and out-of-network hospitalizations.

10.3 Secondary Clinical Outcomes

Secondary outcomes will include the following:

- 1.) 90-day emergency department visit for any cause
- 2.) 90-day death for any cause
- 3.) Composite of 90-day readmission, emergency department visit, or death for any cause
- 4.) 90-day readmission for heart failure
- 5.) 90-day readmission for diabetes-related complication
- 6.) 60-day readmission for any cause
- 7.) 30-day readmission for any cause

KP NOURISH Study Protocol Version 1.0

All utilization outcomes will be assessed passively using the KPNC EHR which comprehensively captures network and out-of-network hospitalizations or emergency department visits. Hospitalizations for heart failure and diabetes-related complications will be assessed using principal discharge ICD-10 diagnosis codes. Deaths will be assessed through a combination of EHR data and external state death certificate data and Social Security Administration vital status file information. In addition, participants' medical records will be manually reviewed by KPNC DOR research staff for participants whose vital status could not be confirmed through follow-up interviews or participant proxy reporting.

10.4 Secondary Patient-reported Outcomes

The following scales will be used for targeted patient-reported outcomes:

- 1.) Change in perceived social isolation (Likert 1-5 scale: Never, Rarely, Sometimes, Often, Always)
 - a. I feel left out.
 - b. I feel that people barely know me.
 - c. I feel isolated from others.
 - d. I feel that people are around me but not with me.
- 2.) Change in perceived self-efficacy (i.e., "How confident are you that you can stick with healthful foods?" Likert 1-10 scale: ranging from Not Confident to Completely Confident)
 - a. Even if you need a long time to develop necessary routines?
 - b. Even if you have to try several times to make it work?
 - c. Even if you have to rethink your entire way of nutrition?
 - d. Even if you have to make a detailed plan?
- 3.) Change in perceived caring (i.e., "My current meals help to create a caring environment that helps me heal": Likert 1-5 scale: Strongly Disagree, Disagree, Neither Agree nor Disagree, Agree, Strongly Agree)

Responses to survey questions will be collected at baseline by phone and at the 10week follow-up phone call conducted by KPNC DOR research staff.

11 Supporting Documentation and Operational Considerations

11.1 Ethical and Administrative Obligations

11.1.1 Regulatory and Ethical Considerations

This clinical study was designed and shall be implemented and reported in accordance with the International Conference on Harmonization (ICH) Harmonized Tripartite Guidelines for Good Clinical Practice (GCP), with applicable local regulations, and with the ethical principles that originate from the Declaration of Helsinki. The protocol must be reviewed and approved by a properly constituted IRB (i.e., the KPNC IRB) before study start. Any amendments to the protocol will require KPNC IRB approval before

implementation of changes made to the study design, except for changes necessary to eliminate an immediate hazard to study patients.

11.1.2 Responsibilities of the Investigator and Good Clinical Practice

These include the following: providing written summaries of the status of the study to the KPNC IRB annually or more frequently in accordance with the requirements, policies, and procedures established by the KPNC IRB and notifying the KPNC IRB of serious adverse events (SAEs) or other significant safety findings as required by IRB procedures. Investigators also will provide careful oversight of the conduct of the study and adhere completely to requirements of ICH guidelines and the IRB for clinical studies (if applicable) and all other applicable local regulations.

11.2 Financial Disclosures

All members of the study team will provide the sponsor (i.e., KPNC DOR) with sufficient and accurate financial information as requested to allow the sponsor to address and disclose potential conflicts of interest.

11.3 Informed Consent Process

Eligible patients will be contacted by phone in their hospital room and asked about their interest in participation in the study during their index hospitalization. Due to Covid-19 restrictions, a waiver of written consent was granted by the KPNC IRB, and all patients interested in participating will be required to provide verbal informed consent. KPNC DOR research staff will explain the purpose of the study, the study procedures, and potential risks and benefits of participation also answer any questions the participant may have before confirming their interest in participating by providing verbal consent.

11.4 Data Collection and Management

11.4.1 Data Confidentiality

Participants will be assigned a unique, encrypted study identifier by the KPNC DOR research team.

Any participant records or datasets will contain the encrypted patient identifier only; patient names or any information which would make the patient identifiable will not be transferred outside of KPNC. Information about study patients will be kept confidential and managed under the applicable laws and regulations. Those regulations require a verbal authorization informing the participant of the following:

- What protected health information (PHI) will be collected from participants in this study
- Who will have access to that information and why.
- Who will use or disclose that information.
- The rights of a research participant to revoke their authorization for use of their PHI.

If a participant revokes authorization to collect or use PHI, the Principal Investigator, by regulation, retains the ability to use all information collected prior to the revocation of participant authorization.

Access to the data will be controlled by a sequence of individually-assigned user identification codes and passwords, made available only to authorized personnel who have completed prerequisite training.

11.4.2 Data Collection

Data pertinent to assessing the study objectives will be automatically abstracted from the EHR by a designated KPNC DOR research team member (i.e., study analyst). Automatic validation programs will check for data discrepancies and generate appropriate data queries to be confirmed or corrected before review of the data by the KPNC DOR research team. Prior to final database lock, the Principal Investigator must certify that the data entered are correct.

11.4.3 Database Management and Quality Control

Data management will be performed by the KPNC DOR research team. Data queries will be raised for any inconsistent, impossible, or missing data. Quality control procedures will be applied to each stage of data handling to ensure that all data are reliable and have been processed correctly. When all data have been coded, validated and locked, a clean file will be declared. Any treatment revealing data may thereafter be added and the final database will be locked.

# 1 Study Overview

| Title                 | Kaiser Permanente Evaluation of Medically tailored Meals in Adults with Chronic Medical Conditions at High Readmission Risk   |
|-----------------------|---|
| Brief Title           | KP NOURISH  |
| Clinical Phase        | Phase III   |
| Investigation
Type | Interventional (Pragmatic)  |
| Study Type            | Prospective, virtual, remote, Electronic Health Record (EHR)-based, parallel-group, randomized, decentralized pragmatic clinical trial (PCT)  |
| Purpose and           | Adults with chronic conditions account for two-thirds of total U.S. health  |
| Rationale             | care expenses. Based on current trends, by 2023, chronic diseases will cost \$4.2 trillion annually in treatment and lost economic output in the U.S. Addressing the social determinants of health can be an effective mechanism for reducing health care costs. Specifically, for adults with chronic illness, previous research has found a correlation between the delivery of certain types of social services and reductions in avoidable hospitalizations. Additionally, existing literature suggests that food insecurity or evidence of poor nutrition are common among individuals at the time of hospital discharge, and particularly among older adults and those with multimorbidity. These individuals may also experience other basic resource needs (inadequate or unsafe housing, transportation barriers, social isolation, etc.) that compound their difficulty in obtaining sufficient and/or nutritious food. Home-delivered meals may thus free up financial resources to address other social needs, reduce social isolation, and reduce transportation demands on the individual and their family. This is even more relevant in California given the impact of the ongoing novel coronavirus disease 2019 (Covid-19) pandemic and associated public health responses (e.g., statewide shelter in place orders enacted in early 2020) and supply chain difficulties, which have collectively introduced additional barriers to obtain healthy food, especially among atrisk individuals. |
|                       | Medically tailored meals (MTMs) provided for a limited time after hospital discharge may help achieve several desirable outcomes. Most directly, they may mitigate food insecurity, social isolation and nutritional deficits related to their nutrition-sensitive chronic medical condition. In turn, these  |
|                       | effects may help vulnerable patients return to a more optimal nutritional status and clinical recovery more quickly after hospital discharge and improve patient and family satisfaction with care at home. The cost of MTMs may also offset use of acute care services (hospitalizations and emergency department [ED] visits) that could potentially be prevented after discharge from the index hospitalization. Given the increasing consideration among health insurers about providing MTMs as a benefit  |

|                    | T  |  |
|--------------------|--|--|
|                    | of enrollment, and recent federal Center for Medicare and Medicaid Services' guidance allowing MTMs as a supplemental benefit in selected populations, there is a pressing need to generate robust evidence about the potential efficacy of MTMs to guide health policy and health care delivery system decision-making.   |  |
| Study Design       | This study is a remote, decentralized, randomized PCT. We will compare outcomes in 3 groups of recently hospitalized patients with a targeted, nutrition-sensitive chronic medical condition (i.e., heart failure, diabetes mellitus or chronic kidney disease): participants receiving MTMs alone, participants receiving MTMs with remotely delivered nutritional counseling, and patients receiving usual standard of care. Participants will be recruited from Kaiser Permanente (KP) Santa Rosa, Santa Clara, Oakland, San Francisco, and San Rafael Medical Centers. The Ceres Community Project (Ceres) will provide MTMs service to patients enrolled at KP Santa Rosa and San Rafael Medical Centers and Project Open Hand (POH) will provide MTMs service to patients enrolled at KP Santa Clara, Oakland and San Francisco Medical Centers.   |  |
| Intervention       | MTMs (with or without remotely delivered nutritional counseling) vs. usual care  |  |
| Inclusion Criteria | 
 
Men and women age ≥18 years at admission to the index hospitalization
 
Hospitalized at KP Santa Rosa, Santa Clara, Oakland, San Francisco, or San Rafael Medical Centers
 
Kaiser Permanente Northern California (KPNC) membership at admission to the index hospitalization
 
Has a prior history of at least one of the following conditions:         
 
Heart failure (defined as ≥3 prior outpatient diagnoses or ≥1 inpatient principal discharge diagnosis or heart failure on current hospital problem list with a corresponding inpatient B-type natriuretic peptide value ≥100 pg/mL)
 
Diabetes mellitus (defined as ≥1 principal inpatient discharge diagnosis within 5 years or ≥2 outpatient diagnoses, excluding optometry and ophthalmology diagnoses, within 5 years or ≥2 abnormal diabetes-related lab test results on separate days within 3 years or ≥1 prescription of a diabetes medication at any time, and not meeting the following exclusions: any diabetes indicator within 8 months before to 1 month after childbirth or a diabetes therapy prescription of metformin or a thiazolidinedione within 2 years after a diagnosis of a non-diabetes metabolic or fertility issue, with no other indication of diabetes.)
 
Chronic kidney disease (defined as ≥2 outpatient estimated glomerular filtration rate [eGFR] values between 30-45 ml/min/1.73 m² within the prior 2 years and the most recent value ≥30 ml/min/1.73 m² within the prior 2 years and the most recent value ≥30 ml/min/1.73 m² on the prior 2 years and the most recent value ≥30 ml/min/1.73 m² on the prior 2 years and the most recent value ≥30 ml/min/1.73 m² on the prior 2 years and the most recent value ≥30 ml/min/1.73 m² on the prior 2 years and the most recent value ≥30 ml/min/1.73 m² on the prior 2 years and the most recent value ≥30 ml/min/1.73 m² on the prior 2 years and the most recent value ≥30 ml/min/1.73 m² on the prior 2 years and the most recent value ≥30 ml/min/1.73 m² on the

 |  |
| Exclusion Criteria | · · · · · · · · · · · · · · · · · · ·  |  |
| Exclusion Criteria | Inability to receive meals delivered to home residence   |  |

|                        | T   |  |
|------------------------|---|--|
|                        | 2. Inability to store or heat food  |  |
|                        | Requiring individual meal customization beyond MTMs                         |  |
| Primary Outcome | Occurrence of an acute hospitalization for any reasons within 90-days       |  |
|                        | after discharge from the index hospitalization.                             |  |
|                        | ·   |  |
| Secondary              | 90-day emergency department visit for any cause                             |  |
| Outcomes               | 2. 90-day death for any cause   |  |
|                        | 3. Composite of 90-day readmission, emergency department visit, or          |  |
|                        | death for any cause   |  |
|                        | 4. 90-day readmission for heart failure                                     |  |
|                        |   |  |
|                        | 5. 90-day readmission for diabetes-related complication                     |  |
|                        | 6. 60-day readmission for any cause   |  |
|                        | 7. 30-day readmission for any cause   |  |
|                        |   |  |
| Clinical Impact        | KP is partnering with two community-based MTMs vendors to evaluate          |  |
| •                      | the effects of MTMs and remotely delivered nutritional counseling on        |  |
|                        | various outcomes of patients with targeted nutrition-sensitive chronic      |  |
|                        | ·   |  |
|                        | medical conditions being discharged to home from KP Santa Rosa,             |  |
|                        | Santa Clara, Oakland, San Francisco, and San Rafael Medical Centers         |  |
|                        | in a randomized controlled trial (RCT) cohort. Due to the projected rise of |  |
|                        | Covid-19 in our patient population within KPNC and the urgency for          |  |
|                        | optimizing care for our most at-risk members, there is a national KP effort |  |
|                        | to implement this study as quickly as possible.                             |  |
|                        | to implement the study do quienty do possible.                              |  |

## 2 Sample Size Calculation

Based on pre-pandemic data from KPNC, the 90-day regional rate of readmission for any reason for adults hospitalized with heart failure is approximately 10-15%. Using this conservative estimate of 10% for the primary outcome of all-cause readmissions among hospitalized adults with heart failure, type 2 diabetes mellitus (hereafter referred to as diabetes) and/or chronic kidney disease who are discharged home, a total sample size of 2000 (1000 assigned to MTMs, 1000 assigned to usual care) and a two-sided  $\alpha$ =0.05 will provide 80% power to detect a hazard ratio of 0.68, corresponding to a 32% relative reduction in the risk of readmission for any cause among participants receiving MTMs versus usual care. Assuming a higher 90-day rate of 20% for a composite outcome (i.e., hospitalization, emergency department visit or death from any cause) and a two-sided  $\alpha$ =0.05, a sample size of 2000 will have 80% power to detect a hazard ratio of 0.76, corresponding to a 24% relative reduction in the risk of this composite outcome among participants receiving MTMs versus usual care.

Comparisons in utilization and survival outcomes between participants receiving MTMs alone compared with MTMs and remotely delivered nutritional counseling are considered exploratory given the limited power to detect clinically meaningful differences. However, given the anticipated total sample sizes of 2000 (1000 assigned to MTMs, 1000 assigned to usual care) or 1000 (500 assigned to MTMs alone, 500 assigned to MTMs with remotely delivered nutritional counseling) and using a two-sided  $\alpha$ =0.05, we will have >80% power to detect even small differences in patient reported outcomes which rely on continuous measures.

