### 4 Efficacy analyses

### 4.1 Primary outcome: Readmission for any cause within 90 days post-discharge

The frequency and risk with associated 95% exact (Clopper-Pearson) binomial confidence intervals (CI) for participants experiencing readmission for any cause within 90 days after discharge from the index hospitalization will be reported by treatment arm. Risk differences will be calculated along with associated Wald 95% CI. Cumulative incidence curves from the cumulative incidence function will be reported descriptively without statistical testing.

The primary measure of association will be the hazard ratio (and associated 95% CI) for MTMs vs Usual Care obtained from a Cox proportional hazards model adjusted for acute severity of illness, predicted short-term readmission risk and multimorbidity burden as well as the presence of active Covid-19 during the index hospitalization, along with any observed additional baseline differences in participant characteristics in the primary analysis population.

The subdistribution hazard ratio (95% CI) for MTMs vs Usual care obtained from Fine and Gray subdistribution hazard models adjusted for acute severity of illness, predicted short-term readmission risk and multimorbidity burden as well as the presence of active Covid-19 during the index hospitalization, along with any observed additional baseline differences in participant characteristics in the primary analysis population will also be reported to examine the effect of MTMs on the cumulative incidence of hospitalizations for any cause accounting for the potential effects of a competing risk of death.

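### SAP section 2: 80% power at HR 0.68 is not reached by the event-driven formula on either reading of the 10% rate (about 71% if usual care, about 78% if pooled)

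*SAP*

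**What the plan says.** SAP section 2 (Sample Size Calculation) starts from pre-pandemic regional data, saying that "the 90-day regional rate of readmission for any reason for adults hospitalized with heart failure is approximately 10-15"%. It plans on the lower end: "Using this conservative estimate of 10% for the primary outcome of all-cause readmissions". With 1000 participants per arm and a two-sided alpha of 0.05, it concludes that the trial "will provide 80% power to detect a hazard ratio of 0.68, corresponding to a 32% relative reduction". For the composite of hospitalization, emergency department visit or death it continues: "Assuming a higher 90-day rate of 20% for a composite outcome", and states that "a sample size of 2000 will have 80% power to detect a hazard ratio of 0.76".

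The section does not say whether 10% and 20% are usual-care rates or averages over both arms. It gives no formula, expected number of events or loss allowance. SAP section 4.1 makes the hazard ratio the primary measure, "obtained from a Cox proportional hazards model adjusted for acute severity of illness" and other factors. Protocol section 7 gives the same total and split (1000 MTMs, 1000 usual care) and no power calculation.

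**The concern.** For a Cox or log-rank comparison, power at a given hazard ratio depends on events, not on participants as such. A 10% rate in 2000 participants gives at most 200 events if it is the average over both arms. It gives fewer if it is the usual-care rate, because the MTMs arm is then assumed to have less than 10%. HR 0.68 needs about 211 events, so the stated inputs and the stated power do not fit together.

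At stake is the trial's headline power statement. The chance of missing a true HR of 0.68 would be about 29% or 22%, depending on the reading, and not the 20% that 80% power implies. A reader also cannot check the statement, because the inputs that would settle it are missing.

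**Working it through.** **Inputs (SAP section 2).** N = 2000, 1:1; two-sided alpha 0.05 (z = 1.960); 80% power (z = 0.842); 90-day rate p = 10% with HR 0.68 (primary) and p = 20% with HR 0.76 (composite). No loss is assumed, since the section states none. The gain or loss from covariate adjustment is ignored, since the section claims none.

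**Formulas.**
- Events needed (Schoenfeld): D = 4 × (1.960 + 0.842)² / (ln HR)².
- Power with D events: Φ(√D/2 × |ln HR| − 1.960).
- MTMs risk when p is the usual-care risk, under proportional hazards: 1 − (1 − p)^HR.

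**Trying to reproduce the primary figure.** ln 0.68 = −0.3857, so D = 4 × 7.849 / 0.1487 ≈ 211 events.

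*10% as the usual-care rate.* MTMs risk = 1 − 0.9^0.68 = 6.91%. Events = 1000 × (0.1000 + 0.0691) ≈ 169. Power = Φ(2.508 − 1.960) = Φ(0.548) ≈ 70.8%. Solving for 80% power gives HR 0.647: MTMs risk 6.59%, about 166 events, √166/2 × 0.435 ≈ 2.80.

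*10% pooled over both arms.* Events = 2000 × 0.10 = 200. Power = Φ(2.727 − 1.960) = Φ(0.767) ≈ 77.8%. The HR with 80% power is exp(−2 × 2.802/√200) = 0.673.

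**Checks on the primary figure.** Freedman's formula gives 69.8% (usual-care reading) and 76.9% (pooled). A log-rank simulation with 4000 runs per scenario gives 70.9% and 78.0%.

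**Composite.** ln 0.76 = −0.2744, so about 417 events are needed.

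| Reading of 20% | Method | Events | Power at 0.76 | Effect with 80% power |
|---|---|---|---|---|
| Pooled | Schoenfeld | 400 | 78.4% | HR 0.756 |
| Usual care | Two proportions, 20% vs 15.2% | – | 80.5% | RR 0.761 |
| Usual care | Schoenfeld (MTMs risk 1 − 0.8^0.76 = 15.6%) | 356 | 73.5% | HR 0.742 |

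The first two rows agree with the SAP's 0.76 after rounding; the third does not.

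**Primary power at HR 0.68 across the SAP's own 10–15% range, taken as usual-care rates.**

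| Usual-care risk | MTMs risk | Events | Power |
|---|---|---|---|
| 10% | 6.9% | 169 | 71% |
| 12.5% | 8.7% | 212 | 80% |
| 15% | 10.5% | 255 | 87% |

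**The case against.** The strongest reply is that the SAP never calls 10% a usual-care rate. On the pooled reading, the HRs with 80% power are 0.673 and 0.756, which are reductions of 32.7% and 24.4%. Cut to whole percentages, these become the stated 32% and 24%. The primary gap would then be about 2 points and a matter of rounding. This is possible and cannot be ruled out. It limits the size of the error but does not remove it: 0.673 rounds to 0.67, and power at the printed 0.68 is still 77.8%.

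Other methods reach 80% for one outcome but do not fit both:
- A two-proportion test with pooled rates (11.9% vs 8.1%) gives 81.1% for the primary, but 86.3% for the composite.
- A two-proportion test with usual-care rates gives 80.5% for the composite, but 73.3% for the primary (10% vs 6.8%).
- A one-sided 0.05 test with usual-care rates gives 80.6% and 82.7%, but the SAP says two-sided.

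Reading 10% as the MTMs-arm rate would give about 85%. That also misses the stated figure, and nothing in the SAP suggests it.

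It is also fair to say that the SAP plans on the low end of its range. The claim holds at a usual-care risk of about 12.5% and is exceeded at 15%. But the statement is tied to 10%, so the higher rates do not make it right.

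A reader might go further and infer that the design simply delivers 71% and 74%, that the composite figure is wrong, or that a null result would be claimed to exclude HR 0.68. The documents support none of these. The first depends on an arm that the SAP does not name. The composite can be reproduced in two ways. The SAP nowhere says that a null result excludes HR 0.68; section 4.1 reports the HR with a 95% confidence interval, which is what shows the effects that are excluded.

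**Conclusion.** The primary power statement is wrong as written for the planned Cox analysis. The shortfall from 80% is about 9 points if 10% is the usual-care rate and about 2 points if it is pooled.

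Usual care is the more natural reading. The 10% comes from pre-pandemic patients who had no study meals, and the 32% reduction is then applied to MTMs against usual care. On the pooled reading the usual-care risk would have to be about 11.8%, so 10% would no longer be the low end of the cited range for untreated patients. The choice between the two remains an inference.

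The composite statement stands unless 20% is declared a usual-care rate and the event-driven formula is used.

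These results assume proportional hazards, full 90-day follow-up and no effect of covariate adjustment on power. This is a correction to a stated figure. It does not affect the analysis, the populations or the validity of the eventual estimate.

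**What to change.** Revise SAP section 2, with no change in enrolment:

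1. State which arm or arms the 10% and 20% describe, the formula and the expected number of events, and use one method for both outcomes.
2. Restate the primary figure to match. If 10% is the usual-care rate: 80% power for HR 0.65, and 71% at HR 0.68. If it is pooled: 80% power for HR 0.67, and 78% at HR 0.68.
3. Restate the composite as 80% power for HR 0.74 only if 20% is declared a usual-care rate and the event-driven formula is used. On the pooled reading, 0.76 can stay.
4. Add the short table of power at HR 0.68 for 10%, 12.5% and 15%, labelled as usual-care rates if that is what they are.

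The sponsor must say which reading it used; the review cannot choose for it. The cost is a few lines of SAP text and a slightly less favourable stated detectable effect.
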